5.2 Subject and trial completion

Approximately 32 subjects will be screened to achieve 24 subjects randomly assigned to two treatment sequences i.e. the default t_{max} setting followed by the non-default t_{max} setting or the non-default t_{max} setting followed by the default t_{max} setting all in combination with fast-acting insulin aspart.

Each subject will have at-least 1 designated contact as per the inclusion criteria 7.

Treatment period completion for a subject:

Treatment period completion is defined as when the randomised subject has received the required treatment as per treatment period 1 and 2 and attended the 'end of treatment' visit according to the flowchart (See section 2).

Trial period completion for a subject:

Trial period completion is defined as when the randomised subject has completed the final scheduled visit ('end of trial' according to the flowchart, see section 2). 'Date of trial completion' is the date the subject completed the final scheduled visit.

5.3 End of trial definition

The end of the trial is defined as the date of the last visit of the last subject in the trial.

5.4 Scientific rationale for trial design

The medical need for using closed-loop medical devices that combine insulin delivery with glucose monitoring is anticipated to be the highest in subjects with T1DM. This is also the patient population with the highest percentage of usage of continuous subcutaneous insulin infusion. For these reasons, this trial will include subjects with T1DM. An escalation trial is chosen since the default t_{\max} setting is going to be investigated along with three non-default t_{\max} settings. A cross-over design is used to enable glycaemic control under non-default t_{\max} settings to be evaluated in a within-subject setting, reducing the impact of between-subject variability.

5.5 Justification for t_{\max} setting

The t_{\max} settings for the trial have been chosen to reflect the default t_{\max} investigated in earlier clinical trials with insulin aspart (t_{65}) and three values below (t_{50} , t_{40} and t_{30}). These values span a range that is expected to include a more optimal t_{\max} setting for the iLet™ using the fast-acting insulin aspart, considering its pharmacokinetic profile⁴.

6 Trial population

Prospective approval of protocol deviations to recruitment and enrolment criteria, also known as protocol waivers or exemptions, is not permitted.

6.1 Inclusion criteria

Subjects are eligible to be included in the trial only if all of the following criteria apply:

1. Informed consent obtained before any trial-related activities. Trial-related activities are any procedures that are carried out as part of the trial, including activities to determine suitability for the trial.
2. Male or female, age ≥ 18 years and ≤ 75 years at the time of signing informed consent.
3. Diagnosed with type 1 diabetes mellitus ≥ 1 year prior to the day of screening.
4. Treated with continuous subcutaneous insulin infusion ≥ 1 year prior to the day of screening.
5. Have a mean total daily dose of insulin ≥ 20 units
6. Familiar with continuous glucose monitoring as judged by the investigator.
7. Has someone over 18 years of age who (i) lives with them, (ii) has access to where they sleep, (iii) is willing to be in the house when the subject is sleeping, and (iv) is willing to receive calls from the study staff and check the welfare of the study subject .
8. BMI ≤ 35.0 kg/m² at screening.
9. HbA_{1c} equal to or below 8.5% (69 mmol/mol) at screening.

10. Able and willing to remain in a designated place for the specified duration of the 'in-patient' periods.
11. Lives within a 120-minute drive away from the central monitoring location (site).

6.2 Exclusion criteria

Subjects are excluded from the trial if any of the following criteria apply:

1. Known or suspected hypersensitivity to trial product or related products
2. Previous participation in this trial. Participation is defined as signed informed consent
3. Female who is pregnant, breast-feeding or intends to become pregnant or is of child-bearing potential and not using an adequate contraceptive method (adequate contraceptive measures as required by local regulation or practice)
4. Participation in any clinical trial of an approved or non-approved investigational medicinal product within 30 days before screening
5. Any disorder, except for conditions associated with diabetes mellitus, which in the investigator's opinion might jeopardise subject's safety or compliance with the protocol
6. Anticipated initiation or change in concomitant medications known to affect weight or glucose metabolism during the trial
7. Impaired liver function, defined as Alanine Aminotransferase (ALT) ≥ 2.5 times or Bilirubin >1.5 times upper normal limit at screening
8. Renal impairment measured as estimated Glomerular Filtration Rate (eGFR) value of eGFR < 60 ml/min/1.73 m²
9. Any episodes of diabetic ketoacidosis within the past 90 days prior to the day of screening
10. Known hypoglycaemic unawareness as indicated by the Investigator according to Clarke's questionnaire question 8^a
11. Recurrent severe hypoglycaemic episodes within the last year as judged by the Investigator
12. Any of the following: myocardial infarction, stroke, hospitalization for unstable angina pectoris or transient ischaemic attack within the past 180 days prior to the day of screening
13. Subjects presently classified as being in New York Heart Association (NYHA) Class IV
14. Planned coronary, carotid or peripheral artery revascularisation known on the day of screening
15. Inadequately treated blood pressure defined as Grade 3 hypertension or higher (Systolic ≥ 180 mmHg or diastolic ≥ 110 mmHg) at screening

^aInformation on hypoglycaemia unawareness will be recorded according to Clarke's questionnaire, question 8⁶. The investigator must ask the subject in the following way: "To what extent can you

tell by your symptoms that your blood glucose is low? Never, Rarely, Sometimes, Often or Always." Subjects answering 'never, rarely or sometimes' are considered to have impaired awareness of hypoglycaemia.

6.3 Lifestyle restrictions

Not applicable for this trial.

6.4 Screen failures

Screen failures are defined as subjects who consent to participate in the clinical trial but are not eligible for participation according to in/exclusion criteria. A minimal set of screen failure information is required to ensure transparent reporting of screen failure subjects to meet requirements from regulatory authorities. Minimal information includes demography, screen failure details, eligibility criteria, and any serious adverse event (SAE).

Individuals who do not meet the criteria for participation in this trial may not be rescreened. Re-sampling is not allowed if the subject has failed one of the inclusion criteria or fulfilled one of the exclusion criteria related to laboratory parameters. However, in case of technical issues (e.g. haemolysed or lost), re-sampling is allowed for the affected parameters.

6.5 Randomisation criteria and dosing day exclusion criteria and run-in exclusion criteria

Not applicable for this trial.

7 Treatments

7.1 Treatments administered

7.1.1 Investigational and non-investigational medicinal products

Trial product must only be used, if it appears clear and colourless.

Table 7–1 Trial products provided by Novo Nordisk A/S

Trial product name:	Fast-acting insulin aspart , 100 U/ml (Investigational medicinal product (IMP), test product)	Fiasp [®] , 100 U/ml (Non- Investigational medicinal product (NIMP))
Dosage form:	Solution for injection	Solution for injection
Route of administration:	Subcutaneous	Subcutaneous
Dosing instructions:	Dosing is handled by iLet [™] autonomously	Dosing as per PI's discretion
Packaging	1.6 mL cartridge (PumpCart [®])	3-mL prefilled insulin pen

		(Fiasp [®] FlexTouch [®])
--	--	--

7.1.2 Medical devices

Investigational medical device(s):

- iLet[™]*: The bionic pancreas including pigtail adapters, used in insulin-only configuration

*For technical complaints (medical device incidents) related to iLet[™] it must be evaluated by the investigator if the technical complaint could have led to an SAE (serious medical device incident) according to Section [9.2.8](#) and [Appendix 6](#).

Information related to the instructions for use of the iLet[™] can be found in the iLet[™] instructional manual.

Beta Bionics will provide the iLet[™] and the StudyPhone with CGM application (app). For complaints related to the iLet[™], the investigator should report it to both Novo Nordisk and Beta Bionics, see [Appendix 6](#). And for complaints related to the Study phone, the investigator must contact Beta Bionics directly.

Non-investigational medical device(s):

- CGM device (Dexcom G5[®]) and its auxiliaries
- StudyPhone with CGM app**
- BG meter (Contour[®] Next One) and its auxiliaries
- Infusion set with 60 cm tube (Contact[™] detach)

Novo Nordisk will provide the aforementioned non-investigational medical devices (except StudyPhone with CGM app) to the subjects along with the paper diary.

For complaints related to the BG meter, infusion set or CGM device, the investigator must contact the device manufacturer's technical support according to Operator's Manuals provided with the BG meter, infusion set and the CGM device.

**StudyPhone with CGM app is an iPhone installed with a CGM app which is used to display the CGM values and to record the SMPGs values for sensor calibration.

Training in the medical devices

At visit 2, investigator should ensure that subjects know how to use the medical devices and perform appropriate training using relevant manuals (as specified in flowchart section [2](#)). The investigator will, as necessary, repeat the trainings at visit 3. The investigator must document all the

trainings in the subject's medical record (such as site record, research record or any other similar document).

The investigator should ensure that the subject knows the following as the minimum:

iLet™

- How to replace the PumpCart®
- How and when to replace the batteries
- Troubleshooting in case of iLet™ failure or any technical problems

CGM – Dexcom G5®

- How and when to change the sensor
- How and when to calibrate the sensor
- How to use the CGM app on StudyPhone

BG Measurement - Contour® Next One

- When to perform self-measured plasma glucose (SMPG) measurements
- How and where to report the SMPG measurements
- How and when to perform ketone measurement

Infusion set – Contact™ detach

- How and when to perform infusion set change
- How to report infusion set change in the diary

7.2 Dose modification

Dose modification is handled autonomously by the iLet™ based on the CGM sensor readings and the user interaction with the iLet™ e.g. meal announcements. Therefore, there is no standard insulin titration algorithm in this trial.

7.3 Method of treatment assignment

Interactive Web Response System (IWRS) will not be used in this trial. All subjects will be assigned a unique number (randomisation number) in ascending numerical order at the trial site. The randomisation number encodes the subject's assignment to one of the treatment sequences of the trial, according to the randomisation schedule generated before the trial.

7.4 Blinding

A single trial product is used in this trial. This is packed open-label; however, the specific treatment sequence for a subject will be assigned using a randomisation list. This will be a single blinded

clinical trial where the participating subjects will be blinded towards the order of their t_{max} setting as this information will not be visible to them.

7.5 Preparation/Handling/Storage/Accountability

Only subjects enrolled in the trial may receive trial product and only authorised site staff may supply or administer trial product.

Table 7–2 Trial product storage conditions

Trial product name	Storage conditions (not-in-use)	In-use conditions	In-use time^a
Fast-acting insulin aspart, 100 U/ml	Store in refrigerator (2°C-8°C) Protect from light Do not freeze	Store below 37°C Protect from light Do not refrigerate Do not freeze	Use within 2 days

^aIn-use time starts when the PumpCart[®] is connected to the iLet[™]

The trial site will be supplied with sufficient trial products for the trial on an on-going basis.

The investigator must confirm that appropriate temperature conditions have been maintained during transit for all trial products received and any discrepancies are reported and resolved before use of the trial products.

All trial products must be stored in a secure, controlled, and monitored (manual or automated) area in accordance with the labelled storage conditions with access limited to the investigator and authorised site staff.

The investigator must inform Novo Nordisk immediately if any trial product has been stored outside specified conditions. Additional details regarding handling of temperature deviations can be found in the Trial Materials Manual (TMM).

Trial product that has been stored improperly must not be dispensed to any subject before it has been evaluated and approved for further use by Novo Nordisk.

The investigator is responsible for drug accountability and record maintenance (i.e. receipt, accountability and final disposition records). Drug accountability should be performed at PumpCart[®] level. Destruction of trial products can be performed on an ongoing basis and will be

done according to local procedures after accountability is finalised by the site and reconciled by the monitor. Destruction of trial products must be documented via site normal procedures.

All returned, expired or damaged trial products (for technical complaint samples see [Appendix 6](#)) must be stored separately from non-allocated trial products. No temperature monitoring is required.

Non-allocated trial products including expired or damaged products must be accounted as unused, at the latest at closure of the trial site.

The CGM sensors distributed to site will have to be stored according to [Table 7-3](#) and temperature monitoring is required.

Table 7-3 Dexcom G5 R CGM sensor storage conditions

Device name	Storage conditions (not-in-use)	In-use conditions	In-use time ^b
Dexcom G5R sensor	Store (2°C – 25°C / 36°F – 77°F) Do not freeze	-	Up to 7 days

^bIn-use time starts when sensor has been fitted

7.6 Treatment compliance

Throughout the trial, the investigator will remind the subjects to follow the trial procedures and requirements to ensure subject compliance. If a subject is found to be non-compliant the investigator will remind the subject of the importance of following the instructions given including taking the trial products as prescribed.

7.7 Concomitant medication

Any medication other than the trial product that the subject is receiving at the time of screening visit or receives during the trial must be recorded along with:

- Trade name or generic name
- Indication
- Dates of administration including start and stop dates

Changes in concomitant medication must be recorded at each visit. If a change is due to an AE/SAE, then this must be reported according to [Section 9.2](#).

7.7.1 Rescue medication

In case of hypoglycaemia, please refer to the section [9.3](#) for treatment of overdose.

In case of hyperglycaemia (e.g. due to pump failure) the subject should be instructed to call the site immediately.

The trial site will supply glucagon (as a part of back-up kit) that will be provided by Novo Nordisk.

The following rescue medications may be used for hypoglycaemia:

1. Ingestion of carbohydrates (e.g. juice)
2. Dextrose
3. Glucagon
4. Parenteral glucose

The rescue medication for hyperglycaemia should be used as per investigator's discretion.

7.8 Treatment after the end of the trial

When discontinuing trial product, the subject should be transferred to a suitable marketed product at the discretion of the investigator.

8 Discontinuation/Withdrawal criteria

The subject may be discontinued at any time during the trial at the discretion of the investigator for safety, behavioural, compliance or administrative reasons. A subject may also withdraw consent at any time at his/her own request.

If a subject is discontinued due to the criteria listed in section [8.1](#), the investigator must ask the subject if he/she is willing, as soon as possible, to have assessment performed according to visit 4 and a phone contact (P 5) after 7 days.

See the flowchart section [2](#) for data to be collected at the time of treatment discontinuation, and follow-up, and for any further evaluations that need to be completed.

8.1 Discontinuation of trial treatment

The subject must be discontinued from trial treatment, if the following applies:

1. Included in the trial in violation of the inclusion and/or exclusion criteria
2. Pregnancy
3. Intention of becoming pregnant
4. Simultaneous participation in another clinical trial of an approved or non-approved investigational medicinal product.

The primary reason for discontinuation of trial product must be specified in the end-of-trial-form in the case report form (CRF), and final drug accountability must be performed.

8.1.1 Escalation stopping criteria

After all subjects have completed Visit 4 in a given cohort, the PI will evaluate if any of the following have occurred in individual subjects:

- Time in low interstitial glucose (defined as below 54 mg/dL (3.0 mmol/L)) is higher than 2% of the total time from initiation of treatment (day 1) to end of treatment (day 7) on the same t_{\max} , or,
- One or more episodes of treatment emergent severe hypoglycaemia (see [Appendix 7](#) for definition) have occurred from initiation of treatment (day 1) to end of treatment (day 7) on the same t_{\max}

For each subject and for each treatment period, the time in low interstitial glucose (percentage) and number of treatment emergent severe hypoglycaemia episodes as per the above evaluation must be recorded in the CRF.

Escalation decision

If any of the above specified events occur in two or more subjects on the same t_{\max} setting within a cohort, continuation to the next cohort with a lower t_{\max} setting will not occur. Concretely, continuation to the next cohort with a lower t_{\max} setting will not occur in the following scenarios:

- Time in low interstitial glucose (defined as below 54 mg/dL (3.0 mmol/L)) is higher than 2% of the total time from initiation of treatment (day 1) to end of treatment (day 7) on the same t_{\max} in two or more subjects,
- One or more episodes of treatment emergent severe hypoglycaemia (see [Appendix 7](#) for definition) have occurred from initiation of treatment (day 1) to end of treatment (day 7) on the same t_{\max} in each of two or more subjects,
- Time in low interstitial glucose (defined as below 54 mg/dL (3.0 mmol/L)) higher than 2% of the total time from initiation of treatment (day 1) to end of treatment (day 7) on the same t_{\max} in one or more subjects and one or more episodes of treatment emergent severe hypoglycaemia (see [Appendix 7](#) for definition) have occurred from initiation of treatment (day 1) to end of treatment (day 7) on the same t_{\max} in one or more subjects.

The escalation decision at the end of the cohort must be documented by the PI. If the escalation decision is to not open the next cohort, then the subjects who are in screening will be registered as withdrawn and an end-of-trial form must be completed.

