9.11 Self-measured plasma glucose

Subjects will be provided with a BG meter including auxiliaries as well as instructions for use. The subjects will be instructed in how to use the device and the instruction should be repeated, if needed

The BG meters use test strips calibrated to plasma values. Therefore, all measurements performed with capillary blood are automatically calibrated to plasma equivalent glucose values, which will be shown on the display.

The BG meter provided by Novo Nordisk should be used for the measurements required in the protocol. SMPGs must be performed to calibrate the CGM sensor (section [9.10](#)) and in the event of hypoglycaemic episode ([Appendix 7](#)) and should be reported in the diary, see section [9.14](#).

All SMPGs values must be recorded in the paper diary. In addition to paper diary, SMPGs performed for the calibration of the CGM sensor must also be recorded on the StudyPhone with CGM app. The record of each SMPG value on paper diary should include date, time and value. All data from the diary must be transcribed into the CRF during or following the contact.

9.12 iLet™ settings

The glucose target for the iLet™ will be set to 120 mg/dL (6.6 mmol/L). Subjects must be instructed not to change any settings related to BW and glucose target on the iLet™. Temporary targets are not allowed.

Initialisation of iLet™

The iLet™ should be initialised by entering the subject's current BW at visit 2 and visit 3. See section [9.4.1](#) for reporting of BW.

The date and time when the site staff starts the iLet™ at visit 2 and visit 3 will be considered as the time-point for initiation of treatment. This start date and time must be recorded in the CRF.

Stopping of iLet™

The date and time when the site staff stops the iLet™ at visit 3 and visit 4 will be considered as time-point for end of treatment. These stop date and time must be recorded in the CRF.

t_{max} setting

The t_{max} setting in the iLet™ should be set by the site staff at visit 2 and visit 3 as per the subject's randomisation sequence.

Meal announcements

Meal announcements can be entered via a user interface that runs on the iLet™. The user interface allows optional meal announcements, designated as “start of the day”, “middle of the day”, or “end of the day” or “sleeping”, of size “tiny”, “small”, “typical for me” or “large”. Subjects will be recommended to use this feature immediately before eating the main meals of the day, but not snacks.

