10.3.1 Primary endpoint

The primary objective of the trial is to investigate the safety of selected t_{\max} settings in the insulin-only configuration of the iLet™ bionic pancreas using fast-acting insulin aspart in adults with T1DM in a short-term, outpatient clinical trial. The primary endpoint to address this objective is:

- Time in low interstitial glucose (defined as below 54 mg/dL [3 mmol/L]) from initiation of treatment (day 1) to end of treatment (day 7) (percentage)

This will be derived as the percentage of available interstitial glucose values below 54 mg/dL (3 mmol/L)

The assessment of the primary endpoint will be based on descriptive summaries presenting mean, median, minimum and maximum values by cohort and treatment.

Supplementary analysis for the primary analysis

The default t_{\max} setting (t_{65}) will be compared to each of the non-default t_{\max} settings (t_{50} , t_{40} and t_{30}) separately by cohort for time spent in low interstitial glucose (defined as below 54 mg/dL [3mmol/L]) using a linear mixed effect model with treatment and period as fixed effects and subject as random effect. This is done to investigate the treatment differences from a within-subject perspective.

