10.3.2 Secondary endpoints

10.3.2.1 Supportive secondary endpoints

Time in interstitial glucose range defined as 70-180 mg/dL (3.9-10 mmol/L) from initiation of treatment (day 1) to end of treatment (day 7) (percentages)

Time in interstitial glucose range defined as 70-180 mg/dL (3.9-10 mmol/L) will be derived as the percentage of available interstitial glucose values above or equal to 70 mg/dL (3.9 mmol/L) and below or equal to 180 mg/dL (10 mmol/L).

It will be presented using descriptive statistics made by cohort and treatment, and analysed using a model similar to the supplementary analysis for the primary analysis.

Mean interstitial glucose level from initiation of treatment (day 1) to end of treatment (day 7) (mg/dL)

The mean interstitial glucose level will be derived as the average of the available interstitial glucose values.

The mean interstitial glucose level will be presented using descriptive statistics made by cohort and treatment, and analysed using a model similar to the supplementary analysis for the primary analysis.

Number of treatment-emergent severe hypoglycaemic episodes from initiation of treatment (day 1) to end of treatment (day 7) (count)

Severe hypoglycaemic episodes are classified according to the ADA definition as described in [Appendix 7](#). Treatment emergent severe hypoglycaemic episodes will be presented in terms of the

number of subjects with at least one episode (N), the percentage of subjects with at least one episode (%), the number of episodes (E) and the episode rate per 100 years of exposure (R) made by cohort and treatment.

Number of treatment emergent hypoglycaemic episodes classified both according to the ADA definition and Novo Nordisk classification from initiation of treatment (day 1) to end of treatment (day 7) (count)

Hypoglycaemic episodes classified both according to the ADA definition and Novo Nordisk classification as described in [Appendix 7](#). Treatment emergent hypoglycaemic episodes will be presented in terms of the number of subjects with at least one episode (N), the percentage of subjects with at least one episode (%), the number of episodes (E) and the episode rate per 100 years of exposure (R) made by cohort and treatment. Separate summaries are made by severity considering all episodes, daytime and nocturnal episodes using Novo Nordisk and ADA classified episodes.

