Number of self-manageable (able to self-treat) treatment-emergent hypoglycaemic episodes that require oral carbohydrate intervention per day from initiation of treatment (day 1) to end of treatment (day 7) (count)

Treatment emergent self-manageable (able to self-treat) hypoglycaemic episodes that require oral carbohydrate intervention per day will be calculated as the sum of all treatment-emergent hypoglycaemic episodes where the subject is able to self-treat and that require oral carbohydrate intervention divided by the actual duration of the treatment period in days. It will be presented using descriptive statistics made by cohort and treatment.

Number of treatment-emergent adverse events from initiation of treatment (day 1) to end of treatment (day 7) (count)

Adverse events will be coded using the Medical Dictionary for Regulatory Activities (MedDRA) and will be presented based on system organ class and preferred terms.

Treatment-emergent: adverse events will be defined as treatment-emergent, if the onset of the event occurs in the on-treatment period

Treatment-emergent adverse events will be presented in terms of the number of subjects with at least one event (N), the percentage of subjects with at least one event (%), the number of events (E) and the event rate per 100 years of exposure (R) made by cohort and treatment. These summaries are done by seriousness, severity, relation to trial product, adverse events leading to discontinuation of trial treatment and outcome.

Furthermore, summary tables based on system organ class and preferred terms are made for:

- All treatment-emergent adverse events
- Serious treatment-emergent adverse events

- Possibly and probably related treatment-emergent adverse events
- Severe treatment-emergent adverse events

All adverse events will be listed with information on when it occurred.

Number of treatment-emergent infusion site reactions from initiation of treatment (day 1) to end of treatment (day 7) (count)

Treatment-emergent infusion site reactions will be summarised by cohort and treatment.

Total insulin dose (U/kg) per day from initiation of treatment (day 1) to end of treatment (day 7) (U/Kg/day)

Total daily insulin dose will be calculated as the sum of all insulin doses delivered by the iLet™ divided by the actual duration of the treatment period in days. It will be presented using descriptive statistics made by cohort and treatment.

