An alert will be generated *after 15 minutes* if remote monitoring for a subject goes offline. *Site staff will contact the subject to troubleshoot the issue and will ask subject to replace the sensor if it is not possible to recover the sensor and/or connectivity within 20-30 minutes.* Site staff will call the subject every 2 hours to check on safety and device function until remote monitoring is restored. If there are no indications of device malfunction as the cause for lost connectivity, the glucose level is in safe range, and a subject chooses to remain in an area with poor network coverage, site staff will instruct the subject to check the iLet™ display or the CGM app (*Dexcom G5®*) on the study phone at least every 20 minutes for alert icons and to be aware that we are unable to monitor for severe lows or highs at this time. *If the subject is unable to establish the CGM connectivity after 6 hours, they should transition to their usual CSII treatment until the Site staff can assess the functionality of the device and the subject’s ability to use it in person.*

Section 9.16.1: Remote Monitoring for Hypoglycaemia

Site staff will verify that the subjects, or their designated contacts, are aware of the hypoglycaemia and are taking action to treat it. Subjects will be reminded of the procedures to follow in case of hypoglycaemia and the site staff will ensure they understand and will follow the procedures. *Subjects will be instructed to measure BG in response to an alarm to verify the CGM reading. If the BG measurement confirms hypoglycaemia, the subjects will be instructed to treat with 15 grams of rapid acting carbohydrates and check the BG again in 15 mins. Subjects will be instructed to treat with another 15 grams of rapid acting carbohydrates if they are still hypoglycaemic. Subjects will be instructed to continue to monitor BG until it returns to ≥ 70 mg/dL (3.9 mmol/L).* Subjects will be encouraged to follow up with any questions or concerns. All contact with the subjects in response to hypoglycaemia alarms will be documented in the subjects’ medical records.

Section 9.16.2: Remote Monitoring for Hyperglycaemia

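### Does the 2% escalation criterion in section 8.1.1 use a different denominator from the primary endpoint in section 10.3.1?

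*Combined protocol and SAP*

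**What the plan says.** Section 8.1.1 has the principal investigator review each subject after the cohort has completed visit 4. One of the two subject-level criteria is time below 54 mg/dL that "is higher than 2% of the total time from initiation of treatment (day 1) to end of treatment (day 7" on one t_max setting. The percentage for each subject and period "as per the above evaluation must be recorded in the CRF". The cohort rule begins "If any of the above specified events occur in two or more subjects on the same" setting, in which case the next cohort does not open.

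Section 10.3.1 gives the derivation of the primary endpoint, which has the same cut-off and interval: "This will be derived as the percentage of available interstitial glucose values below 54 mg/dL (3 mmol/L"). Section 10.3.2.1 treats time in range the same way: it "will be derived as the percentage of available interstitial glucose values above or equal to 70 mg/dL (3.9 mmol/L") up to an upper limit of 180 mg/dL. Table 10-1 follows the same pattern.

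Section 9.12 ties the interval to the clock: the moment site staff stop the iLet "at visit 3 and visit 4 will be considered as time-point for end of treatment". Section 10.3.4.3 tabulates the stopping criteria by reference to 8.1.1 and names no denominator.

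**The concern.** Read word by word, the same quantity has two denominators. *Total time* between two recorded clock times sounds like elapsed time, while section 10.3.1 divides by what the sensor delivered. The plan does divide by elapsed time elsewhere: total insulin dose is "divided by the actual duration of the treatment period in days". Section 8.1.1 does not cite 10.3.1, and none of the four amendments touches the point.

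CGM gaps are foreseen. Under Amendment 1, section 9.16: "If the subject is unable to establish the CGM connectivity after 6 hours, they should transition to their usual CSII treatment". Temporary discontinuation (section 8.1.2) and the sensor's 7-day life (section 9.10) are other sources.

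If missing time entered the denominator but never the numerator, the 8.1.1 figure would be at or below the endpoint figure, and any disagreement would favour opening the next cohort. With eight subjects per cohort and a two-subject rule, one reclassified subject could change an escalation decision in a trial whose primary objective is safety.

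**Working it through.** **What the wording supports.** The plan states no figure to reproduce here, so the first step is to compare the passages.

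- The primary endpoint is itself titled as a *time* from start to end of treatment, expressed as a percentage, and is then derived from available values (10.3.1).
- Table 10-1 does this in two columns: the left names a time in a glucose range, the right computes it from available values.
- Section 8.1.1 uses the endpoint's name, cut-off and interval. Section 9.1 says that quantities based on the glucose profile come from the iLet data.
- The elapsed-time phrase used for insulin dose does not appear in 8.1.1.

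*Total time* therefore reads most naturally as the whole treatment period, as opposed to the in-patient part (section 9.15) or the out-patient part (section 10.3.4.2), which the plan also examines.

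**What a literal reading needs.** Let T be the readings expected in the period, A those available, L the low ones, and m = 1 − A/T the missing fraction.

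- Section 10.3.1: L/A.
- Elapsed time, missing counted as not low: L/T = (1 − m) × L/A. This is never above L/A.
- Elapsed time, missing assumed to resemble the observed time: [L + (L/A)(T − A)]/T = L/A. This is identical to 10.3.1.

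An elapsed-time denominator alone does not create the difference. A second rule is needed, that unobserved time is not low, and no section states it.

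**Size if that rule were applied.** Inputs: threshold 2% (8.1.1); period of 7 days (5.1); 6 hours (Amendment 1, section 9.16). The 5-minute reading interval is an assumption, since the protocol gives only a 5-minute dosing step (3.2.1). The documents give no expected missingness, so 5% and 10% are also assumptions.

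T = 7 × 288 = 2016. Since 0.02 × 2016 = 40.32, the literal rule needs at least 41 low readings. On available values the trigger is the first whole number above 0.02A. The two disagree up to 2%/(1 − m) of available values.

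| Missing | A | 0.02A | Trigger on available values | Discordant counts | Upper edge, % of available |
|---|---|---|---|---|---|
| none | 2016 | 40.32 | 41 | none | 2.00 |
| 6 h (72 readings) | 1944 | 38.88 | 39 | 39–40 | 2.07 |
| 5% (8.4 h) | 1915 | 38.30 | 39 | 39–40 | 2.11 |
| 10% (16.8 h) | 1814 | 36.28 | 37 | 37–40 | 2.22 |

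At 10% missing, 37 low readings are 37/1814 = 2.04% of available values and 37/2016 = 1.84% of the total; 40 are 2.21% and 1.98%.

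The visit window allows a period one day shorter. Then T = 6 × 288 = 1728 and the literal trigger is 35 (0.02 × 1728 = 34.56). With a 6-hour gap, A = 1656 and the available-value trigger is 34 (0.02 × 1656 = 33.12), so only a count of 34 is discordant.

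Conversely, a subject at x% of available values drops to 2% of 168 hours only if 168 × (1 − 2/x) hours are missing: 8.0 hours at 2.1%, 15.3 hours at 2.2% and 33.6 hours at 2.5%.

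**The case for a change.** The strongest case for a change is about timing. The investigator applies 8.1.1 after each cohort, whereas section 10.3 makes a separate SAP optional and due only before database lock. A later SAP could not guide those decisions, and a gate between cohorts should not depend on which section is read. With gaps, the CRF entry and the endpoint derived from iLet data could also carry two values under one name.

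The absence of a link between the sections stands. It is also true that 6 hours is not a ceiling on missing time: it is the point at which a subject leaves the iLet, and readings may be absent for longer. What does not stand is the inference that the plan sets two rules. An investigator looking for how to compute the percentage finds one method, in 10.3.1.

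Long gaps are also worked against: monitoring runs around the clock (9.16), and under Amendment 1 an offline alert comes after 15 minutes and the sensor is replaced if it cannot be recovered within 20–30 minutes.

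How time off the iLet is counted is a separate detail. Limiting the criterion to one t_max setting gives some ground for leaving that time out, but the on-treatment definition in 10.2 does not address interruptions. The question arises equally for 10.3.1 and so is not a conflict between the two sections.

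**Conclusion.** The concern does not call for a change. Section 8.1.1 describes the percentage in words of time and section 10.3.1 says how it is calculated, which is the plan's usual pattern. A cross-reference would be tidy, but the escalation evaluation can be carried out soundly without it.

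With complete CGM data the two readings agree exactly. A difference requires both an elapsed-time denominator and an unstated rule that missing time is not low. For one 6-hour gap the affected band is then 2.00–2.07% of available values. To alter an escalation decision, a subject must fall in that band while exactly one other subject on the same setting meets a criterion. The severe-hypoglycaemia criterion is unaffected.

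These sizes rest on assumed 5-minute readings and a full 168-hour period. Much larger gaps would widen the band, but the documents give no basis for expecting them. No view is taken on the 2% threshold or on the escalation rule itself.
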